4.8 Statistical Software, Reporting and Technical details

All analyses will be conducted using Stata Statistical software $(v17)^7$ or later. Appendix B Table 3 provides the proposed template for the statistical analysis of the primary and secondary outcomes. These results may also be presented graphically, where appropriate. Any post-hoc explanatory analyses not identified in the SAP will be clearly identified in the final statistical report. Any deviations from the planned analyses detailed in the SAP will be documented and reported in a revised version of this SAP.

5. References

- 2. Royal Australian College of General Practitioners. *Guidelines for preventive activities in general practice.* 9th ed. East Melbourne: RACGP; 2017.
- 3. Kidney Health Australia. *Chronic kidney disease (CKD) management in general practice.* Melbourne: Kidney Health Australia; 2015.
- 4. Alliance NVDP. *Guidelines for the management of absolute cardiovascular disease risk.* 2012.
- 7. *Stata Statistical Software: Release 17*. College Station, TX: StataCorp LLC.; 2021.
- 8. Australian Bureau of Statistics. Socio-Economic Indexes for Areas 2011; https://www.abs.gov.au/websitedbs/censushome.nsf/home/seifa.
- 11. Agresti A. Categorical data analysis / Alan Agresti. In. 3rd ed: Wiley-Interscience; 2013.

Appendix A – CONSORT diagram

Appendix B – Proposed tables for Baseline Participant Characteristics and Outcomes

Table 1. Base	line characteristics	of practices and	practice staff for all	participants and b	v study arm
Table 1. Dase		or practices and	practice starrior an	participants and b	y study ann

	All participants	Intervention arm	Active control arm
Practice Characteristics	N	N	N
State			
Victoria	n(%)	n(%)	n(%)
Tasmania	n(%)	n(%)	n(%)
Relative Socio-Economic Disadvant	age Index (Terciles)		
1 Most disadvantaged	n(%)	n(%)	n(%)
2	n(%)	n(%)	n(%)
3 Least disadvantaged	n(%)	n(%)	n(%)
Previously participated in QI	n(%)	n(%)	n(%)
Program			
Practice Size			
4 or fewer FTE GPs	n(%)	n(%)	n(%)
Greater than 4 FTE GPs	n(%)	n(%)	n(%)
Number of FTE GPs	Median (IQR)	Median (IQR)	Median (IQR)
Number of FTE Nurses	Median (IQR)	Median (IQR)	Median (IQR)
Number of FTE Practice	Median (IQR)	Median (IQR)	Median (IQR)
Managers/Administrative staff			
General practitioners	Ν	Ν	Ν
Sex			
Male	n(%)	n(%)	n(%)
Female	n(%)	n(%)	n(%)
Age			
< 35 years	n(%)	n(%)	n(%)
35 to 50 years	n(%)	n(%)	n(%)
> 50 years	n(%)	n(%)	n(%)
Registered nurses	Ν	Ν	Ν
Sex			
Male	n(%)	n(%)	n(%)
Female	n(%)	n(%)	n(%)
Age			
< 35 years	n(%)	n(%)	n(%)
35 to 50 years	n(%)	n(%)	n(%)
> 50 years	n(%)	n(%)	n(%)
Practice managers/	Ν	Ν	Ν
Administrative staff			
Sex			
Male	n(%)	n(%)	n(%)
Female	n(%)	n(%)	n(%)
Age			
< 35 years	n(%)	n(%)	n(%)
35 to 50 years	n(%)	n(%)	n(%)
> 50 years	n(%)	n(%)	n(%)

N – number of practices/practice staff; % - Column percentage; IQR – Interquartile range; FTE – Full-time equivalent; GP - general practitioner. **Note**: Continuous variables may be categorised and sub-categories may also be collapsed in final table published.

Patient Characteristics	All participants	Intervention arm	Control arm
	Ν	Ν	Ν
Sex			
Male	n(%)	n(%)	n(%)
Female	n(%)	n(%)	n(%)
Other	n(%)	n(%)	n(%)
Age (years)	mean (SD)	mean (SD)	mean (SD)
Prescribed ACEI/ARB			
ACEI only	n(%)	n(%)	n(%)
ARB only	n(%)	n(%)	n(%)
ACEI and ARB	n(%)	n(%)	n(%)
None	n(%)	n(%)	n(%)
Prescribed Statins			
Yes	n(%)	n(%)	n(%)
No	n(%)	n(%)	n(%)
Recommendation for guidelin	e concordant care to conside	er initiating:	
Both ACEI/ARB & statins	n(%)	n(%)	n(%)
ACEI/ARBs only	n(%)	n(%)	n(%)
Statin only	n(%)	n(%)	n(%)
CVD Risk Category			
Low	n(%)	n(%)	n(%)
Moderate	n(%)	n(%)	n(%)
High	n(%)	n(%)	n(%)
SBP (mmHg)	N mean (SD)	N mean(SD)	N mean(SD)
Lipids (all mmol/L)			
Total	N mean(SD)	N mean(SD)	N mean(SD)
LDL	N mean(SD)	N mean(SD)	N mean(SD)
HDL	N mean(SD)	N mean(SD)	N mean(Sd)
Triglycerides	N mean(SD)	N mean(SD)	N mean(SD)
uACR (mg/g)	N mean(SD)	N mean(SD)	N mean(SD)
eGFR (ml/min/1.73 ²)	N mean(SD)	N mean(SD)	N mean(SD)

Table 2. Baseline characteristics of patients for all participants and by study arm

N – number of patients; % - Column percentage; SD – standard deviation

Note: Continuous variables may be categorised and sub-categories may also be collapsed in final table published.

Table 3. Analyses for Primary and Secondary Outcomes

	All	Intervention	Active	Estimated effect size		
	participants	ailli	arm			
Primary Outcome	Ν	Ν	N			
Primary analysis	n (%)	n (%)	n (%)	Difference (95% CI)	Odds ratio (95% CI)	p-value
Sensitivity Analysis ¹				Difference (95% CI)	Odds ratio (95% CI)	p-value
Sensitivity Analysis ²				Difference (95% CI)	Odds ratio (95% CI)	p-value
Adherence adjusted analysis ³				Difference (95% CI)	Odds ratio (95% CI)	p-value
Secondary outcomes	N	N	N			
(1, 2, and 6)						
Primary analysis	n (%)	n (%)	n (%)	Difference (95% CI)	Odds ratio (95% CI)	p-value
Sensitivity Analysis ¹				Difference (95% CI)	Odds ratio (95% CI)	p-value
Sensitivity Analysis ²				Difference (95% CI)	Odds ratio (95% CI)	p-value
Secondary Outcomes	Ν	Ν	Ν			
(3, 4, 5 and 8)						
Primary analysis	mean (SD)	mean (SD)	mean (SD)	Difference in m	ieans (95% CI)	p-value
Sensitivity Analysis ¹				Difference in m	ieans (95% CI)	p-value
Sensitivity Analysis ²				Difference in m	ieans (95% CI)	p-value
Secondary Outcome 7	N	Ν	Ν			
Primary analysis				Cumulative Odd	s ratio (95% CI)	p-value
Low CVD risk	n (%)	n (%)	n (%)			
Medium CVD risk	n (%)	n (%)	n (%)			
High CVD risk	n (%)	n (%)	n (%)			
Sensitivity Analysis ¹				Cumulative Odd	s ratio (95% CI)	p-value
Sensitivity Analysis ²				Cumulative Odd	s ratio (95% CI)	p-value
Secondary Outcome 9	N	N	N			
Primary analysis	n (rate)	n (rate)	n (rate)	Difference in rates (95% CI)	Rate ratio (95% CI)	p-value
Sensitivity Analysis ¹				Difference in rates (95% Cl)	Rate ratio (95% CI)	p-value
Sensitivity Analysis ²				Difference in rates (95% CI)	Rate ratio (95% CI)	p-value

N – number of patients; Difference – Difference in percentages between the arms, unless otherwise stated; SD - Standard deviation; % - column percentages; CI -Confidence interval.

¹ Sensitivity analysis adjusted for the practice participation in formalised QI program, patients age in year, and patient's sex

² Sensitivity analysis for intercurrent events

1.1 Synopsis

Future Health Today (FHT) is a stratified head-to-head cluster randomised controlled trial (RCT) of quality improvement (QI) activities in general practice in Australia. The QI program that forms the intervention consists of a new technology platform (FHT, with audit, recall, clinical decision support and monitoring of QI activity capability) and case-based learning series for specific clinical areas. For the FHT trial we have focused on QI programs for two common conditions managed in general practice, cancer-risk and chronic kidney disease (CKD). The QI cancer-risk program focuses on the appropriate investigation and follow-up of people at increased risk of an undiagnosed cancer among general practice patients. The QI CKD program focuses on reducing cardiovascular disease (CVD) risk for individuals with a recorded diagnosis or pathology results consistent with a diagnosis of CKD. General practices will be randomly assigned equally to either the QI CKD program or the QI cancer-risk program. Thus, practices randomised to the QI cancer-risk program will act as an active control for the QI CKD program, and vice versa.

This statistical analysis plan (SAP) will focus on the cancer-risk intervention and a separate SAP was developed documenting the statistical analysis for the CKD intervention. The analysis and findings for each study (CKD and cancer-risk) will be published as separate manuscripts following the CONSORT (Consolidated Standards of Reporting Trials) guidelines.¹ The background and rationale for the FHT trial are described in the trial protocol, including the setting, recruitment, eligibility criteria, randomisation, and sample size calculations.

This document elaborates on the statistical analysis for the primary and secondary outcomes of the cancer-risk intervention, including sensitivity and pre-planned explanatory analyses, health economic analyses and handling of missing outcome data where appropriate. The process evaluation to identify the barriers and facilitators to successful implementation of FHT in daily practice will be described in a separate document.

1.2 Primary hypothesis

The null hypothesis is that there is no difference in the proportion of patients, identified as at risk of an undiagnosed cancer, who receive guideline concordant follow-up at 12 months post-intervention compared with patients attending general practice providing usual care (active control arm) The alternative hypothesis is that there is a difference in the primary outcome between the two trial arms.

1.3 Study objectives

The cancer-risk trial component will evaluate the effectiveness of the FHT QI intervention on the appropriate investigation and follow-up of people at increased risk of an undiagnosed cancer in general practice.²⁻⁵ The primary objective is to determine if patients with abnormal test results and additional clinical features placing them at risk of an undiagnosed cancer who attend general practice clinics participating in FHT QI for cancer-risk (intervention arm) are more likely than similar patients attending general practices that provide usual care (control arm) to be assessed and investigated within 12 months post-randomisation.

Secondary objectives of the trial are to determine the effectiveness of the FHT QI program for cancer risk compared to usual care for patients by evaluating the:

- proportion of patients with markers of anaemia ((Haemoglobin <130g/L in men and <115g/L in women) or MCV <80fl or MCH <27pg or ferritin<30µg/L) that have been assessed for upper and lower GI symptoms and/or haematuria or who have had at least one of the following investigations ordered during the 12-month follow-up period post-randomisation: a repeat full blood count, iron studies, coeliac disease serology, faecal occult blood test (FOBT), transvaginal ultrasound or a referral for further investigation.^{2,6}
- proportion of patients with markers of anaemia that have a prescription of oral supplements and/or had an iron infusion recorded in the general practice electronic medical record (EMR) during the 12-month follow-up period post-randomisation.⁷
- 3. proportion of patients with a raised platelet count that have been assessed for symptoms (defined in Victorian Department of Health³, NICE², and Cancer Council⁴ guidelines as indicative of oesophageal, gastric, colorectal, endometrial, lung or ovarian cancer) or who have been followed up with one or more of the following during the 12-month follow-up period post-randomisation: a repeat platelet count, chest x-ray, chest CT, FOBT, transvaginal ultrasound, CA125, or a referral for further investigation.
- 4. proportion of patients with one raised PSA that have been followed up with a second PSA and/or free-to-total PSA percentage (as per Cancer Council Australia guidelines⁴) or a referral for further investigation, during the 12-month follow-up period post-randomisation.^{5,8}
- 5. proportion of patients with an altered test result placing them at risk of an undiagnosed cancer (iron-deficiency anaemia, raised platelets or raised PSA) who have a diagnosis of prostate, oesophageal, gastric, colorectal, endometrial, lung or ovarian cancer during the 12-month follow-up period post-randomisation.
- 6. rate of encounters per patient identified as at risk of undiagnosed prostate, oesophageal, gastric, colorectal, endometrial, lung or ovarian cancer over the 12 months post-randomisation.
- 7. time to investigation for patients who have an altered test result placing them as at increased risk of an undiagnosed cancer during the trial period, using the first relevant investigation to occur between the patient's entry into the trial and 12-months post-randomisation.

For the health economic analysis, the objective is to quantify the costs of the delivery of the FHT QI program and the health care service costs. Specifically, the objectives are:

- 8. to estimate the cost of the FHT software program installation for QI and cost of training for general practitioners to use the software.
- 9. examine primary health service utilisation and cost incurred by patients identified as at risk of cancer in the intervention arm compared to at risk patients in the active control arm over the 12-month period post-randomisation.

2 Trial design

The FHT trial is a stratified head-to-head cluster randomised controlled trial. The unit of randomisation is the general practice, where practices are randomly allocated concurrently on 1:1 ratio to either participate in the FHT Cancer-risk module (intervention arm) or FHT CKD QI module (active control arm). All general practices will be provided access to the respective QI programs at the commencement of the trial (October 4th, 2021). The active control arm described in this SAP will receive a QI program aimed at optimising pharmacological management in people with CKD to reduce cardiovascular disease (CVD) risk. Please refer to the trial protocol for a detailed description of the intervention and comparator.

2.1 Study Population

The trial will be conducted in general practices in Victoria and Tasmania. For full details of the eligibility and exclusion criteria for general practices, please refer to the study protocol.

2.2 Patient eligibility and exclusion criteria

Eligible patients will be identified as at risk of cancer by applying at least one or more of the following criteria:

At baseline – 4th October (**closed cohort**):

- Patients aged 50 to 80 years (inclusive) without a recorded GI, unspecified or metastatic cancer in the last 5 years who have one marker of anaemia (defined as Hb <130g/L in men and <115g/L in women or MCV <80fl or MCH <27pg or ferritin<30µg/L) in the past 6 months or two consecutive markers of anaemia in the past 12 months.
- 2. Males aged 40 to 80 years (inclusive) without a recorded diagnosis of lung, colorectal, gastrooesophageal or unspecific cancer in the previous 5 years or females aged 40 to 80 years old without a diagnosis of lung, colorectal, gastro-oesophageal, ovarian, endometrial or unspecific cancer in the previous 5 years who have one elevated plated count (defined as platelet count > 400×10^{9} /L) in the past 6 months or two consecutive elevated platelets counts in the past 12 months.
- 3. Males, aged 40-80, without a recorded diagnosis of prostate cancer with a raised PSA (defined as male aged 40-49 PSA > 2.0 ng/ml; male aged 50+ PSA> 3.0 ng/ml) in the past 6 months.

4th Oct 2021 - 4th April 2022 (**open cohort**):

- 4. Eligible patients not captured at baseline, with one or more markers of anaemia between October 4, 2021, and April 4, 2022.
- 5. Eligible patients not captured at baseline with an elevated platelet count between October 4, 2021, and April 4, 2022.
- 6. Eligible patients not captured at baseline with an elevated PSA between October 4, 2021, and April 4, 2022.

The terms closed and open cohort refer to when the patients were identified as at risk of cancer: at baseline, or during the first 6-months of the trial, respectively. Subsequent references to the closed and open cohorts refer to these eligibility criteria and the timeframes used to identify these patients.

Exclusions:

- 1. Patients that are recorded as no longer active in the general practice or deceased in the EMR.
- 2. Patients that are pregnant at baseline.

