4.1 Primary outcome

The **primary outcome** is the proportion of eligible patients identified as at risk of undiagnosed prostate, oesophageal, gastric, colorectal, endometrial, lung or ovarian cancer that have been assessed and investigated according to NICE², Cancer Council Victoria⁴, Victorian Government Department of Health and Human Services⁸, Prostate Cancer Foundation of Australia guidelines⁵, within the 12-month trial period. The absence of any relevant recorded investigation, prescription, observation, or diagnosis during the trial period will be considered equivalent to the patient not being assessed or investigated.

The primary outcome will include any relevant investigation, dependent on whether patients were identified as at risk of cancer for iron deficiency anaemia, raised platelets or raised PSA. The relevant investigation must occur between being identified as at risk of an undiagnosed cancer (either at baseline or within the following 6 months), and the trial end date (30th Sept 2022).

For each patient identified as at risk of cancer with one or more markers of anaemia, a relevant investigation includes a repeat full blood count, iron studies, coeliac disease serology, FOBT, transvaginal ultrasound, referral to gastroenterologist, assessment of upper or lower GI symptoms and/or haematuria, prescription of an oral supplement and/or record of an iron infusion.

For each patient identified as at risk of cancer with a raised platelet count, a relevant investigation includes a repeat platelet count, chest x-ray, chest CT, FOBT, CA-125, transvaginal ultrasound, assessment for symptoms for lung, colorectal, gastro-oesophageal, ovarian or endometrial cancer, referral to a gastroenterologist, respiratory physician, or gynaecologist.

For each patient identified at risk of cancer with a raised PSA, a relevant investigation includes a repeat PSA test, free to total PSA percentage and/or referral to a urologist.

For any patient identified as at risk of cancer with more than one altered test result (e.g., anaemia and raised platelets), we will consider a relevant investigation from either marker as the equivalent of being assessed and investigated according to guidelines. In usual care, it is expected that the GP would prioritise care or use a sequential manner in responding to multiple possible investigations.

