4.5 Supplementary analyses

4.5.1 Sensitivity analyses 1: Adjustment of additional covariates

Sensitivity analysis of primary and secondary outcomes will additionally adjust for four confounders measured at baseline: prior practice participation in a formalised quality improvement program (yes, no), patient's' age at entry into the cohort, sex (male, female, other) and whether they were identified in the open or closed cohort. These variables will be added as covariates to the regression models described for the primary analysis.

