4.5.7 Exploratory/sub-group analyses

To evaluate the shorter time for follow-up in the open cohort, we will conduct a sub-group analysis in patients identified as at risk of an undiagnosed cancer, using the sub-groups of those identified at baseline (closed cohort), compared with those identified in the first 6 months after the trial start date (open cohort). Further sub-group analyses will be conducted for the primary outcome, such as the appropriate investigation for sex (male, female, other) and age at entry into the cohort. These exploratory analyses may be reported in part with the primary analysis or in a separate publication.

The statistical analysis for each subgroup will be conducted by including the subgroup variable and its interaction with the intervention as fixed effects to the regression models. Summary statistics will be presented for each sub-group within each study arm, as well as estimates for the intervention effects (appropriate to the outcome type) with a 95% confidence interval and a p-value corresponding to the

interaction term between the study arm and the subgroup variable. The estimates may also be displayed graphically using forest plots.

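### The cancer-risk primary analysis pools patients identified after the modules went live, while the estimate in patients identified at baseline is left to an exploratory subgroup

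*SAP*

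**What the plan says.** All references are to the cancer-risk SAP.

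- **Allocation and access (section 2).** General "practices are randomly allocated concurrently on 1:1 ratio", and "All general practices will be provided access to the respective QI programs at the commencement of the trial (October 4th, 2021".
- **Cohorts (2.2).** The closed cohort rests on abnormal results in the 6 or 12 months before 4 October 2021. The open cohort adds "Eligible patients not captured at baseline, with one or more markers of anaemia between October 4, 2021, and April 4, 2022", with parallel entries for platelets and PSA. The section explains: "The terms closed and open cohort refer to when the patients were identified as at risk of cancer", that is, at baseline or during the first six months.
- **Primary outcome (4.1).** Both cohorts count: "The relevant investigation must occur between being identified as at risk of an undiagnosed cancer (either at baseline or within the following 6 months". Follow-up closes for everyone on 30 September 2022.
- **Primary model (4.4.4).** Besides arm, the covariates are GP FTE and IRSD tercile. Cohort is not among them.
- **Sensitivity analysis 1 (4.5.1).** It "will additionally adjust for four confounders measured at baseline", the fourth being "whether they were identified in the open or closed cohort". Footnote 1 to Table 3 in Appendix B describes the same analysis with three covariates (QI participation, age, sex) and omits cohort.
- **Subgroup (4.5.7).** "To evaluate the shorter time for follow-up in the open cohort", effects in the closed and open cohorts are compared through an interaction term. The analysis is exploratory and may be reported with the primary analysis or elsewhere.
- **Outcome 7 (4.2, 4.4.5).** Time to investigation is analysed in the open cohort only.

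**The concern.** Randomising practices protects a comparison of patients only if the patients are defined without reference to anything the allocation could have changed. The closed cohort meets that condition, because its qualifying results predate module access. The open cohort need not. A patient enters it only if a blood count, ferritin or PSA result was recorded and was abnormal while the practice had its allocated program. If testing differs between arms, the denominators can differ in number, in type of patient, or in both. Part of a difference in the pooled proportion would then reflect who was tested, not how abnormal results were followed up.

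The plan does not name this risk. Its closed-versus-open comparison is motivated only by shorter follow-up, and it calls cohort a baseline variable when, by the definition in 2.2, cohort is settled during the trial. Outcome 7 has no closed-cohort counterpart to fall back on.

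**Working it through.** The SAP gives no sample size, follow-up rate or ICC for the cancer-risk study, so there is no figure to reproduce. The dates come from the document. All other inputs below are assumptions.

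**1. Timing.** Module access and open-cohort entry both start on 4 October 2021.
- Entry window, 4 October 2021 to 4 April 2022: 182 days, none of them before access.
- Follow-up to 30 September 2022: 361 days for closed patients, 179 to 361 days for open patients.

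**2. Only the number of open patients differs by arm.** Assume no true effect, with follow-up of 60% in closed and 45% in open patients in both arms. Assume an open share of 38% in one arm and 30% in the other, which means (0.38/0.62)/(0.30/0.70) = 1.43 times as many open patients per closed patient.
- Pooled proportions: 0.62×0.60 + 0.38×0.45 = 0.543, and 0.70×0.60 + 0.30×0.45 = 0.555.
- Spurious difference: −1.2 points. Within each cohort the arms are equal, so adjusting for cohort removes it entirely.

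**3. The type of open patient differs by arm.** Assume no true effect and 60% follow-up in both cohorts. The open share of the control pool is *s* = 0.3 or 0.5. One arm identifies a further fraction *x* = 0.1 to 0.5 of open patients, whose follow-up probability is *p* = 0.4 or 0.8. Put E = *s·x*.
- Pooled difference = E(*p* − 0.60)/(1 + E). For *s* = 0.3, *x* = 0.1, *p* = 0.4: 0.03×(−0.20)/1.03 = −0.58 points. For *s* = 0.5, *x* = 0.5: 0.25×(−0.20)/1.25 = −4.00 points.
- Open-cohort difference = [*x*/(1 + *x*)](*p* − 0.60): −1.82 points at *x* = 0.1, −6.67 at *x* = 0.5.
- Cohort-adjusted difference = open-cohort difference × w_open/(w_open + w_closed), where w_closed = (1 − *s*)/2 and w_open = *s*(*s* + E)/(2*s* + E). For *s* = *x* = 0.5: 0.30/(0.30 + 0.25) × (−6.67) = −3.64 points. For *s* = 0.3, *x* = 0.1: −0.56 points.
- With *p* = 0.8 every sign reverses. With *p* = 0.6 every difference is 0. The closed-cohort difference is 0 throughout.

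Steps 2 and 3 show why the cohort covariate is only a partial remedy: it removes a difference in mix between cohorts but little of a difference in who is in the open cohort.

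**4. Precision of a closed-cohort estimate.** With the same practices and outcome variance, SE ratio = √[v(m₁)/v(m₂)], v(m) = [1 + (m − 1)ICC]/m, where m₁ is closed and m₂ all patients per practice.
- For (m₁, m₂) = (100, 150), (50, 75) and (100, 200), with ICC 0.02 to 0.10, the ratio runs from √(0.1090/0.1060) = 1.014 to √(0.0396/0.0331) = 1.094.
- The less favourable pair (50, 100) at ICC 0.02 gives √(0.0396/0.0298) = 1.153.

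**The case against.** **The mechanism is not documented.** Section 2.5 describes the module as running algorithms over existing records to flag patients who may need follow-up, so it acts once an abnormal result exists. The CKD module concerns drug treatment. No passage says that either module prompts first-time blood counts, ferritin or PSA. Eligibility is derived by algorithm from extracted data, by analysts masked to arm, not by clinicians choosing whom to enter. All of this stands, and it is why the point is a risk and not a finding of bias. It does not remove the risk: the program also includes audit, recall and case-based learning (1.1), on different conditions in the two arms, and these could plausibly alter testing.

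**Results are dated, orders are not.** Section 2.2 dates the abnormal marker. A reader might infer that every open-cohort test was ordered under the influence of a module, but some early results may come from tests ordered before 4 October 2021.

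**The primary model does not condition on cohort.** A reader might infer from 4.5.1 that the main result adjusts for a post-randomisation variable. Under 4.4.4 it does not; that happens only in sensitivity analysis 1.

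**Much is already planned.** Table 2 gives numbers and characteristics by arm within each cohort, and 4.5.7 will produce a closed-cohort effect with a confidence interval. This is real protection. What is missing is a guarantee that the closed-cohort estimate appears with the main result, and a count of qualifying tests by arm.

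**Newly identified patients belong to the target.** Sections 2.2 and 4.1 deliberately include them, and outcome 7 needs an index result within the trial. This argues against removing them from the primary analysis.

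**Conclusion.** The point holds as a risk. Part of the primary denominator is defined after allocation and module access and could depend on arm. The estimate protected by randomisation is planned only as an exploratory subgroup with an optional place of publication. Calling cohort a variable measured at baseline is wrong under the SAP's own definition, and 4.5.1 and the Table 3 footnote disagree about whether it is fitted.

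The possible size, 0.6 to 4.0 points pooled and 0.6 to 3.6 after cohort adjustment, rests wholly on assumed shares and follow-up probabilities. It is zero if the extra patients resemble the others, and its sign is unknown. These figures do not predict what the trial will show.

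A reader might go further and conclude that the pooled analysis is invalid or that the closed cohort must replace it. The documents do not support that: no arm difference in testing is shown, and the replacement would narrow the stated target population.

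**What to change.** Keep the pooled primary analysis and amend the cancer-risk SAP before analysis starts:

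- **4.5:** add a named sensitivity analysis restricted to the closed cohort, for the primary outcome and outcomes 1 to 5, using the 4.4.4 models. Report it in the main paper beside the pooled result and give identification after allocation as the reason.
- **4.4.2:** report by arm, per practice, the number of qualifying tests (blood counts, ferritin, PSA) done in the entry window and the number of open-cohort entries.
- **4.5.1:** describe cohort as a post-randomisation variable, and show sensitivity analysis 1 with and without it. It is constant for outcome 7 and drops out there. Make footnote 1 of Table 3 agree.
- **4.4.5:** state that outcome 7 rests on the open cohort alone and is open to identification bias.

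The cost is SAP wording, one more row per outcome in Table 3 and one count of tests; the closed-cohort effect on the primary outcome should already come out of 4.5.7. The closed-cohort estimate will be somewhat less precise: SE about 1% to 9% larger for three assumed pairs of cohort sizes, and about 15% if 50 of 100 patients per practice are closed and the ICC is 0.02. The precision of the primary estimate does not change.
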